3.6 CRITERIA FOR REMOVAL FROM PROTOCOL THERAPY AND OFF STUDY CRITERIA

Prior to removal from study, effort must be made to have all subjects complete a safety visit a minimum of 2-4 weeks following the last dose of study therapy in person or via telephone/videocall or other NIH approved remote platform as detailed in Section 3.5.4.

3.6.1 Criteria for Removal from Protocol Therapy

- Patient refusal of further treatments.
- It is deemed in the best interest of the patient.
- A patient who develops a concurrent serious medical condition that might preclude or contraindicate the further administration of mithramycin will be removed from treatment.
- Progressive disease.
- A patient who becomes pregnant will be immediately taken off therapy.
- Excessive toxicity as defined in Section 3.3.
- Failure to meet criteria for additional treatment as defined in Section 3.4.

Note: Patients will be followed until toxicity resolves to less than or equal to Grade 1 or baseline (as detailed in Section 3.5.4).

3.6.2 Off-Study Criteria

- Voluntary withdrawal for any reason, or noncompliance with protocol requirements.
- Completion of the follow-up period (see Section 3.5.4).
- Progressive disease with no ongoing treatment related toxicities above Grade 1 or baseline.
- If the investigator determines that it is in the best interest of the patient to discontinue follow up.
- Investigator decision to end study.
- Lost to follow up.
- Death.

4 CONCOMITANT MEDICATIONS/MEASURES

4.1 HEMATOLOGIC AND BLOOD PRODUCT SUPPORT

Blood product support should be provided to maintain platelets > 20,000 cells/mcl, Hgb > 8.0 gm/dl and as clinically indicated. Growth factor support is not permitted with exception of administration of filgrastim. Filgrastim will not be administered prophylactically, but may be administered during Cycle 1 if a patient experiences neutropenic sepsis, or during subsequent cycles if clinically indicated.

4.2 ANTIEMETIC THERAPY AND TRANSAMINITIS PROPHYLAXIS

Additional antiemetic therapy will be prescribed using clinical standard of care practices, per the discretion of the Principal Investigator. The provided antiemetic therapy may be either intravenous or oral route as needed. (See Section 3.2 for antiemetic therapy prior to mithramycin infusion.)

4.3 ANTIDIARRHEALS

Antidiarrheal agents will be prescribed using standard clinical practice guidelines at the preference of the investigator.

4.4 ELECTROLYTE REPLACEMENT

Electrolyte replacement will be provided to maintain serum levels within normal limits.

5 CORRELATIVE STUDIES / BIOSPECIMEN COLLECTION

5.1 PHARMACOKINETIC (PK) SAMPLING

Detailed plasma pharmacokinetic (PK) sampling of mithramycin will be collected as outlined in [Appendix 3](#). PK analysis will be performed in the NCI, Genitourinary Malignancies Branch (GMB). Samples will be stored in the Thoracic Epigenetics Lab (TEL) and batched and later transferred to the [name] Lab on dry ice for analysis.

5.2 STUDIES ON TUMOR TISSUE

Tissue biopsies will be obtained by minimally invasive methods such as CT guided percutaneous, endoscopic, laparoscopic or video-assisted thoracoscopic techniques at baseline* if sufficient tissue is not available from a previous biopsy (all efforts will be made to avoid repeat biopsy) and on Cycle 1 Day 4 (\pm 3 days). If possible, an optional biopsy may be taken at treatment evaluation

following Course 1. If insufficient tissue was obtained or if there was harm associated with the first biopsy, a second biopsy will not be obtained. Should a patient experience a dramatic clinical response to treatment, additional tumor tissue biopsies may be requested, but are not required (refer to [Appendix 2](#)). At the time of tissue acquisition, immediate on-site cytopathologic analysis will be performed to confirm that malignant cells are present in the biopsies, to enhance potential yield and improve subsequent evaluation of molecular endpoints. Samples will be placed in saline in an orange top tube on wet ice and transported to the Thoracic Epigenetics Lab for further processing.

In the Thoracic Epigenetics Lab, a portion will be separated and frozen on dry ice for RNA collection for focused microarray and/or qRT-PCR analysis of ~50 genes modulated by mithramycin in murine xenograft experiments. If sufficient tissue is available, another portion will be imbedded in paraffin for subsequent immunostaining experiments, focusing on expression of genes correlating with treatment response in our preclinical experiments. Additional tissue will be used to establish cell lines to examine effects of mithramycin on the epigenome and stem cell signaling *in vitro*, in an attempt to correlate these findings with results obtained from analysis of tumor biopsies, or to examine SP. All of the analyses, which are predicated on acquisition of sufficient biopsy materials, will be performed in the Thoracic Epigenetics Lab under direction of the PI.

Note: If there is an optional biopsy for research in the protocol, then the patient will consent at the time of the procedure. If the patient refuses the optional biopsy at that time, the refusal will be documented in the medical record and in the research record.

* May be omitted as outlined in [Appendix 2: Study Calendar](#).

5.3 SAMPLE STORAGE, TRACKING AND DISPOSITION

Samples will be ordered in CRIS and tracked through Clinical Trial Data Management system. Should a CRIS screen not be available, the CRIS downtime procedures will be followed. Samples will not be sent outside NIH without appropriate approvals and/or agreements, if required.

5.3.1 Thoracic Epigenetics Laboratory

This study will be conducted within the Thoracic Surgery Branch, NCI. Sample collection and initial processing will be performed in the Thoracic Epigenetics Laboratory. Samples will be stored in designated monitored freezers (at least -20°C). All samples obtained on this study will be tracked using Labmatrix. Pharmacokinetic samples will be analyzed in the [name] Lab, GMB. Samples will be identified and tracked using unique identifiers linked to each subject's unique patient number (study number). Codes linking personal identifiable information to the unique identifier will be stored in secure, computer servers with limited coded access or locked file cabinets in the Thoracic Surgery Branch, NCI with access limited to the PI or study coordinator. Focused gene expression microRNA, and DNA methylation signatures will be analyzed in [name] laboratory using a panel of genes and miRs that were noted to be modulated in subQ cancer xenografts following IP mithramycin treatment.

5.3.2.2 Sample Data Collection

All samples sent to the Blood Processing Core (BPC) will be barcoded, with data entered and stored in the Labmatrix utilized by the BPC. This is a secure program, with access to Labmatrix limited to defined [name] lab personnel, who are issued individual user accounts. Installation of Labmatrix is limited to computers specified by [name]. These computers all have a password restricted login screen.

Labmatrix creates a unique barcode ID for every sample and sample box, which cannot be traced back to patients without Labmatrix access. The data recorded for each sample includes the patient ID, name, trial name/protocol number, time drawn, cycle time point, dose, material type, as well as box and freezer location. Patient demographics associated with the clinical center patient number are provided in the system. For each sample, there are notes associated with the processing method (delay in sample processing, storage conditions on the ward, etc.).

5.3.2.3 Sample Storage and Destruction

Sample bar-codes are linked to patient demographics and limited clinical information. Barcoded samples are stored in barcoded boxes in a locked freezer at either -20 or -80°C according to stability requirements. These freezers are located onsite in the BPC and offsite at NCI Frederick Central Repository Services in Frederick, MD. Visitors to the laboratory are required to be accompanied by laboratory staff at all times.

Access to stored clinical samples is restricted. Samples will be stored until requested by a researcher named on the protocol. All requests are monitored and tracked in Labmatrix. All researchers are required to sign a form stating that the samples are only to be used for research purposes associated with this trial (as per the IRB approved protocol) and that any unused samples must be returned to the BPC. It is the responsibility of the NCI Principal Investigator to ensure that the samples requested are being used in a manner consistent with IRB approval.

If, at any time, a patient withdraws from the study and does not wish for their existing samples to be utilized, the individual must provide a written request. Following receipt of this request, the samples will be destroyed (or returned to the patient, if so requested). The PI will record any loss or unanticipated destruction of samples as a deviation. Reporting will be per the requirements of Section [7.2](#).

5.3.3 Protocol Completion/Sample Destruction

All specimens obtained in the protocol are used as defined in the protocol. Any specimens that are remaining at the completion of the protocol will be stored in the conditions described below. The study will remain open so long as sample or data analysis continues.

If the patient withdraws consent the participants data will be excluded from future distributions, but data that have already been distributed for approved research use will not be able to be retrieved.

Following completion of this study, if the subject has co-enrolled on 06C0014, samples will be transferred to the Tissue Procurement protocol and remain in storage in the Blood Processing Core (BPC) as detailed within 06C0014. Access to these samples will only be granted following IRB approval of an additional protocol, granting the rights to use the material. If the subject has not co-enrolled on the Tissue Procurement protocol, the samples will be destroyed.

The PI will record any loss or unanticipated destruction of samples as a deviation. Reporting will be per the requirements of Section [7.2](#).

6 DATA COLLECTION AND EVALUATION

6.1 DATA COLLECTION

For the purposes of the research sample analyses and correlation with clinical outcomes, demographic information, histology, operative and peri-operative interventions, pathologic findings, laboratory and imaging parameters (performed as part of routine or protocol specified patient care) may be collected on this study. The PI will be responsible for overseeing entry of data into an in-house password protected electronic system (C3D, Labmatrix) and ensuring data accuracy, consistency and timeliness. The principal investigator, associate investigators/research nurses and/or a contracted data manager will assist with the data management efforts. All data obtained during the conduct of the protocol will be kept in secure network drives or in approved alternative sites that comply with NIH security standards. Primary and final analyzed data will have identifiers so that research data can be attributed to an individual human subject participant.

All AEs, including clinically significant abnormal findings on laboratory evaluations, regardless of severity, will be followed until return to baseline or stabilization of event.

Document AEs from the first study intervention, Study Day 1, through 2-4 weeks after the last dose of study therapy. Beyond 2-4 weeks after the last intervention, only adverse events which are serious and related to the study intervention need to be recorded.

An abnormal laboratory value will be considered an AE **only** if the laboratory abnormality is characterized by any of the following:

- Results in discontinuation from the study
- Is associated with clinical signs or symptoms
- Requires treatment or any other therapeutic intervention
- Is associated with death or another serious adverse event, including hospitalization
- Is judged by the Investigator to be of significant clinical impact
- If any abnormal laboratory result is considered clinically significant, the investigator will provide details about the action taken with respect to the test drug and about the patient's outcome.

End of Study Procedures: Data will be stored according to HHS, FDA regulations, and NIH Intramural Records Retention Schedule as applicable.

Loss or Destruction of Data: Should we become aware that a major breach in our plan to protect subject confidentiality and trial data has occurred, this will be reported expeditiously per requirements in Section 7.2.1.

6.1.1 Routine Data Collection

Following registration, all adverse events will be described in the source documents, reviewed by the designated research nurse, and captured in C3D.

- During hospitalization, only the admission labs, first morning labs drawn after 4 am, and labs that support the diagnosis of a reportable event will be uploaded into C3D.
- During chemotherapy regimen, for laboratory values obtained at sites other than the NIH Clinical Center: only the following values will be captured in C3D:
 - Hemoglobin, total white blood cell count, absolute neutrophil count, platelet count
 - PTT, PT or INR
 - Creatinine, ALT, AST, Bilirubin (total and direct), lipase and amylase
 - Any unexpected laboratory abnormality \geq Grade 2 possibly, probably or definitely related to the research
- During the follow up period (more than 30 days following the last treatment), only those events that are serious, unexpected, and related to the treatment will be captured in C3D.
- All toxicities occurring within 30 days of treatment will be followed until resolution to Grade 1 or return to baseline.

6.1.2 Exclusions to Routine Data Collection

6.1.2.1 Adverse Events

The following Adverse Events will be captured only in the source documents and will not be reported in C3D:

- Laboratory values that do not support the diagnosis of a reportable event.
- All Grade 1 events, except for bleeding events, which will all be captured regardless of grade.

6.1.2.2 Concomitant Medications/Measures

All concomitant medications and measures will be captured in the source documents. Only those medications that the patient is taking at baseline on a routine basis or medications that cause an AE will be captured in C3D (e.g., onetime medications, PRN medications, supportive medications, electrolyte replacement and medications given to treat adverse events will not be captured in C3D).

6.2 DATA SHARING PLANS

6.2.1 Human Data Sharing Plan

What data will be shared?

I will share human data generated in this research for future research as follows:

- Coded, linked data in an NIH-funded or approved public repository.
- Coded, linked data in BTRIS (automatic for activities in the Clinical Center).

How and where will the data be shared?

Data will be shared through:

- An NIH-funded or approved public repository, clinicaltrials.gov.
- BTRIS (automatic for activities in the Clinical Center).
- Publication and/or public presentations.

When will the data be shared?

- Before publication.
- At the time of publication or shortly thereafter.

6.2.2 Genomic Data Sharing Plan

The study is not subject to the NIH genomic data sharing policy. The gene, microRNA and DNA methylation studies performed under this protocol are not genome wide.

6.3 RESPONSE CRITERIA

For the purposes of this study, patients should be re-evaluated for response every 8 weeks (1 course) (± 2 weeks). In addition to a baseline scan, confirmatory scans should also be obtained not less than 4 weeks following initial documentation of objective response.

Response and progression will be evaluated in this study using the new international criteria proposed by the revised Response Evaluation Criteria in Solid Tumors (RECIST) [(Version 1.1)(80)]. Changes in the largest diameter (unidimensional measurement) of the tumor lesions and the shortest diameter in the case of malignant lymph nodes are used in the RECIST criteria.

Note: Lesions are either measurable or non-measurable using the criteria provided below. The term “evaluable” in reference to measurability will not be used because it does not provide additional meaning or accuracy.

6.3.1 Disease Parameters

Measurable disease: Measurable lesions are defined as those that can be accurately measured in at least one dimension (longest diameter to be recorded) as:

- By chest x-ray: ≥ 20 mm;
- By CT scan:
 - Scan slice thickness 5 mm or under: as ≥ 10 mm
 - Scan slice thickness > 5 mm: double the slice thickness
- With calipers on clinical exam: ≥ 10 mm.

All tumor measurements must be recorded in millimeters (or decimal fractions of centimeters).

6.3.1.1 Malignant Lymph Nodes

To be considered pathologically enlarged and measurable, a lymph node must be ≥ 15 mm in short axis when assessed by CT scan (CT scan slice thickness recommended to be no greater than 5 mm). At baseline and in follow-up, only the short axis will be measured and followed.

6.3.1.2 Non-Measurable Disease

All other lesions (or sites of disease), including small lesions (longest diameter < 10 mm or pathological lymph nodes with ≥ 10 to < 15 mm short axis), are considered non-measurable disease. Bone lesions, leptomeningeal disease, ascites, pleural/pericardial effusions, lymphangitis cutis/pulmonitis, inflammatory breast disease, and abdominal masses (not followed by CT or MRI), are considered as non-measurable.

Note: Cystic lesions that meet the criteria for radiographically defined simple cysts should not be considered as malignant lesions (neither measurable nor non-measurable) since they are, by definition, simple cysts.

‘Cystic lesions’ thought to represent cystic metastases can be considered as measurable lesions, if they meet the definition of measurability described above. However, if non-cystic lesions are present in the same patient, these are preferred for selection as target lesions.

6.3.1.3 Target Lesions

All measurable lesions up to a maximum of 2 lesions per organ and 5 lesions in total, representative of all involved organs, should be identified as **target lesions** and recorded and measured at baseline. Target lesions should be selected on the basis of their size (lesions with the longest diameter), be representative of all involved organs, but in addition should be those that lend themselves to reproducible repeated measurements. It may be the case that, on occasion, the largest lesion does not lend itself to reproducible measurement in which circumstance the next largest lesion which can be measured reproducibly should be selected. A sum of the diameters (longest for non-nodal lesions, short axis for nodal lesions) for all target lesions will be calculated and reported as the baseline sum diameters. If lymph nodes are to be included in the sum, then only the short axis is added into the sum. The baseline sum diameters will be used as reference to further characterize any objective tumor regression in the measurable dimension of the disease.

Progressive disease by RECIST criteria (80) noted after the first re-staging scan may represent disease that was not detected on the pre-study scan, and a confirmatory scan will be required at the next scheduled re-staging evaluation unless clinically not indicated. If confirmed, progression should be dated by the initial time when the lesions are first detected. If progressive disease by RECIST criteria is seen after Cycle 2, but not confirmed on subsequent restaging scan, the scans from after Cycle 2 would serve as the baseline scan to evaluate for disease progression (81).

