3 STUDY IMPLEMENTATION

3.1 STUDY DESIGN

This Phase I/II study is designed primarily to evaluate the toxicities, pharmacokinetics and clinical efficacy of mithramycin administered as a continuous 24-hour infusion in patients with thoracic malignancies. All patients will be evaluated initially in the Thoracic Surgery Clinic, Clinical Center, NIH. Once appropriate consents have been signed, patients will undergo biopsy of their tumors for analysis of pharmacodynamics endpoints via endoscopic procedures performed in the operating room by the Thoracic Surgery attending physicians or by percutaneous FNA methods performed by interventional radiology staff at the Clinical Center, NIH. Specimens will be processed for DNA/RNA isolation, and immunohistochemistry studies. If sufficient materials are available from a previous biopsy either at the NIH or elsewhere, this baseline biopsy may be omitted as outlined in [Appendix 2](#). Patients will be hospitalized on 3NW, NIH Clinical Center, and receive 24h infusions of mithramycin as outlined below using a conventional Phase I study design, with no intra-patient dose escalation, and no routine cytokine support. Treatment cycles will be separated by 2 weeks to allow recovery from systemic toxicities. Due to potential cardiac toxicity related to mithramycin, all patients will have EKGs (12 lead) prior to, and daily EKGs for 4 days following mithramycin infusions (first cycle only unless otherwise clinically indicated), and will be on telemetry during the Cycle 1 infusion (and subsequent cycles if clinically indicated per Cardiology recommendations). Patients will also have routine bloodwork as outlined in [Section 3.5](#). Blood will be obtained at designated time points to assess mithramycin levels are outlined in [Section 5.1](#). Unless medical difficulties arose during the collection of the first biopsy, a post-treatment tumor biopsy will be obtained on Cycle 1 Day 4 (+/- 3 days) to assess molecular endpoints. At the time of each biopsy session, representative samples will be evaluated by frozen section techniques to verify the histology and quality of the tumor tissue for subsequent analysis. An attempt will be made to biopsy the same tumor site for consistency of sampling during the treatment cycles. Approximately 14 days following initiation of the first treatment cycle, a second treatment cycle will commence. If possible, an optional tumor biopsy may be taken at treatment evaluation following the end of Course 1, and additional optional tumor biopsies requested if a patient experiences a dramatic clinical response to treatment, provided that the biopsies are easy to obtain and pose little risk to the patients (refer to [Section 5.2](#) and [Appendix 2](#)). CT guided research biopsies will not exceed 5 per year on this study. At the end of the fourth cycle (approximately 56-60 days following the initiation of the first treatment cycle), patients will return to the Thoracic Surgery Clinic for repeat staging studies and blood work to analyze treatment response using criteria outlined in [Section 6.3.3](#). In patients who exhibit response to therapy and commence a second course of mithramycin treatment an additional tissue biopsy may be requested during this course of therapy for confirmatory analysis of pharmacodynamics endpoints identified in preclinical experiments to be associated with regressions of human cancer xenografts in mice.

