3.2 DRUG ADMINISTRATION

Given our recent findings within our recent Phase II mithramycin trial (12C0151) pertaining to ABCB4, ABCB11, RALBP and CYP8B1 SNPs that distinguish patients who did and did not experience mithramycin-mediated hepatotoxicity, this protocol will accrue only those patients with favorable ABCB4/ABCB11/RALBP/CYP8B1 genotypes.

Mithramycin will be administered intravenously via central line over 24 hours once every 14 days (+7 days/-3 days). 12 mg IV of dexamethasone will be administered one hour prior to each infusion. Four cycles will constitute one course. Intravenous hydration will be provided as clinically indicated.

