6.3.2.2 Metastatic Bone Lesions

Disease progression is considered if any new lesion is observed on bone scan. New lesions seen by the end of Cycle 2 or before Cycle 3 (with the first re-staging bone scan) may represent disease that was not detected on the pre-study scan, and a confirmatory scan will be required at the next scheduled re-staging bone scan unless clinically not indicated. If confirmed, progression should be dated by the initial time when the lesions are first detected. If new lesions are seen after Cycle 2, but no additional lesions are seen on confirmatory scans, the scans from post-Cycle 2 would serve as the baseline scan to evaluate for disease progression (80).

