6.3.3 Response Criteria for Radiographic Studies

6.3.3.1 Measuring of Soft Tissue Disease

a. Evaluation of Target Lesions

Complete Response (CR)

Disappearance of all target lesions. Any pathological lymph nodes (whether target or non-target) must have reduction in short axis to < 10 mm.

Partial Response (PR)

At least a 30% decrease in the sum of the diameters of target lesions, taking as reference the baseline sum diameters.

Progressive Disease (PD)

At least a 20% increase in the sum of the diameters of target lesions, taking as reference the smallest sum on study (this includes the baseline sum if that is the smallest on study). In addition to the relative increase of 20%, the sum must also demonstrate an absolute increase of at least 5 mm. (Note: The appearance of one or more new lesions is also considered progressions.)

Note: For this study, determination of PD will not be made prior to the Day 60 evaluation.

Stable Disease (SD)

Neither sufficient shrinkage to qualify for PR nor sufficient increase to qualify for PD, taking as reference the smallest sum diameters while on study.

b. Evaluation of Non-Target Lesions

Complete Response (CR)

Disappearance of all non-target lesions and normalization of tumor marker level. All lymph nodes must be non-pathological in size (<10 mm short axis).

Note: Tumor markers alone cannot be used to assess response. If tumor markers are initially above the upper normal limit, they must normalize for a patient to be considered in complete clinical response.

Non-CR/Non-PD (Stable Disease, SD)

Persistence of one or more non-target lesion(s) and/or maintenance of tumor marker level above the normal limits.

Progressive Disease (PD)

Appearance of one or more new lesions and/or *unequivocal progression* of existing non-target lesions. *Unequivocal progression* should not normally trump target lesion status. It must be representative of overall disease status change, not a single lesion increase.

Although a clear progression of “non-target” lesions only is exceptional, the opinion of the treating physician should prevail in such circumstances, and the progression status should be confirmed at a later time by the review panel (or Principal Investigator).

c. Evaluation of Best Overall Response

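### The unconfirmed-progression rule in 6.3.1.3 and 6.3.2.2 is tied to Cycle 2 scans that are not scheduled, and for target-sum growth its re-baselining contradicts the smallest-sum rule in 6.3.3.1

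*Combined protocol and SAP*

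**What the plan says.** **The unconfirmed-PD rule.** Section 6.3.1.3 asks that PD found at the first restaging be confirmed at the next scheduled restaging, because it may be disease that the pre-study scan missed. For PD seen after Cycle 2 and not confirmed, "the scans from after Cycle 2 would serve as the baseline scan to evaluate for disease progression". Section 6.3.2.2 applies the same idea to bone: "New lesions seen by the end of Cycle 2 or before Cycle 3 (with the first re-staging bone scan") need confirmation. If no further lesions appear, "the scans from post-Cycle 2 would serve as the baseline scan to evaluate for disease progression".

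**The schedule.** Infusions run "over 24 hours once every 14 days (+7 days/-3 days"), four cycles to a course. Section 3.1 places the first restaging "At the end of the fourth cycle (approximately 56-60 days following the initiation of the first treatment cycle"). Section 6.3 and Appendix 2 (footnote i) give the same interval, 8 weeks with a 2-week margin either side. Appendix 2 lists CT of chest, abdomen and pelvis, PET/CT and brain MR. It lists no bone scan.

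**The general PD rule.** Section 6.3.3.1 states that "determination of PD will not be made prior to the Day 60 evaluation". It defines target-lesion PD as growth of at least 20% (and at least 5 mm), "taking as reference the smallest sum on study (this includes the baseline sum if that is the smallest on study"). It adds: "The appearance of one or more new lesions is also considered progressions". The best-overall-response text and section 6.3.4 also take the smallest measurements since the start of treatment as the PD reference.

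**Removal and retreatment.** The Précis, 3.1.2.1 and 3.6.1 end treatment or study participation on progression. Section 3.4 allows a further course only with stable or responding disease. Follow-up imaging in 3.5.4 and Appendix 2 (footnote h) covers stable or responding patients. None of these texts mentions confirmation. Section 3.4 points to section 6.2 for progression, but 6.2 is Data Sharing Plans.

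**The concern.** There are three faults.

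1. **Timing.** The rule acts on scans at a point in the schedule where there are none and where PD may not be called. The words in 6.3.2.2 that place the first restaging before Cycle 3 contradict the calendar outright.

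2. **Reference.** If the first restaging is meant, and PD came from growth of the target sum, 6.3.1.3 compares later scans with an enlarged sum. Section 6.3.3.1 compares them with the smallest sum and states no exception. The same scans can then be PD under one section and stable disease under the other.

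3. **Alignment.** Confirmation waits for the next restaging, about one course later. As written, the removal and retreatment rules stop treatment at the first PD, and follow-up imaging leaves out the patient who needs the confirming scan.

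At stake are consistent PD calls and the decision to give up to four more infusions of a drug that caused Grade 4 ALT/AST elevations in the first three patients (3.1.2.1). For the primary endpoint the exposure is narrow, but the Phase II decisions turn on single responses (1 of 7, then 3 of 21), so the rule should be fixed beforehand.

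**Working it through.** **Timing.** The inputs are the 14-day cycle and four-cycle course (Précis), the infusion window of -3/+7 days (3.2), the 8-week interval with its 2-week margin (6.3), and the Day 60 bar (6.3.3.1).

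- First restaging: 4 × 14 = Day 56, which agrees with the stated 56-60 days. The margin gives 56 - 14 = Day 42 to 56 + 14 = Day 70.
- End of Cycle 2: 2 × 14 = Day 28, nominally 60 - 28 = 32 days before Day 60.
- End of Cycle 2 with the infusion window: 2 × 11 = Day 22 to 2 × 21 = Day 42. The latest value touches the opening of the restaging margin, but a scan then would still precede Day 60.

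**Reference, for growth of the target sum.** The PD threshold is 1.20 × the reference sum. The 5 mm minimum is met throughout. The sums are assumed: baseline 100, first restaging 125, second 115, third 130 mm. Unconfirmed is taken to mean a second sum below 120 mm, since the protocol does not define it. The confirmation step is taken as given, so the 125 mm scan does not itself end follow-up.

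| Rule | Reference (mm) | PD at (mm) | Third scan, 130 mm |
|---|---|---|---|
| 6.3.3.1, smallest sum | 100 | 1.20 × 100 = 120 | +30%, PD |
| 6.3.1.3, literal reset | 125 | 1.20 × 125 = 150 | 130/125 = +4%, not PD |
| 6.3.1.3, if a later low replaces the reset | 115 | 1.20 × 115 = 138 | 130/115 = +13%, not PD |

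The literal reset therefore allows growth of 50% over the smallest sum. The third row needs a rule that 6.3.1.3 does not state.

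Varying the second sum, with the first restaging held at 125 mm:

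| Second sum (mm) | PD at, smallest sum | PD at, literal reset | PD at, later low |
|---|---|---|---|
| 119 | 120 | 150 | 142.8 |
| 115 | 120 | 150 | 138 |
| 110 | 120 | 150 | 132 |
| 105 | 120 | 150 | 126 |
| 95 | 1.20 × 95 = 114 | 150 | 114 |

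A third sum from the smallest-sum threshold up to the reset threshold is called differently by the two sections. For second sums of 100 mm or less the references coincide only on the later-low reading.

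**Bone lesions and new lesions.** Bone lesions are non-measurable (6.3.1.2) and have no sum, so the reference conflict does not arise in 6.3.2.2, nor for PD from new lesions alone. There the faults are the Cycle 2 timing, a bone scan that is not on the calendar, and an unstated exception to the rule that a new lesion is PD.

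**Primary endpoint.** PR is measured from the original baseline in every section. Best response runs until progression, so it depends on this rule only if first-restaging PD is followed by a confirmed fall of at least 30% from baseline, here to 0.70 × 100 = 70 mm or less.

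**The case against.** **The timing and reference faults are alternatives.** If Day 28 is meant, the rule never operates and resets nothing. If the first restaging is meant, the timing fault is a wrong label. This is right, and the point is built that way. An end-of-Course-1 scan is also, literally, after Cycle 2, so 6.3.1.3 can be fitted to the schedule. Section 6.3.2.2 cannot, because it says before Cycle 3.

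**The rule is meant for lesions missed at baseline.** The stated rationale in 6.3.1.3 does concern undetected disease, and for new lesions alone there is no reference conflict. But the trigger is PD by RECIST criteria without restriction, which includes growth of the target sum. The rule could be read as a specific exception to the general one. If so, 6.3.3.1 and 6.3.4 should say so, and the reference sum after the reset should be named.

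**The clash with 6.3.4 is slight.** Duration applies only to responders. If a later low replaces the reset, a responder's reference is the same low under both rules. On the literal reset it is not: a sum of 70 mm gives PD at 1.20 × 70 = 84 mm against 150 mm.

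**The consequences are small.** No duration or time-to-progression endpoint appears in the objectives or section 10, and under 10.2 a patient observed on therapy for a full course is evaluable whether or not PD is called. This stands and limits the severity.

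A reader might infer that a patient awaiting confirmation has no stated treatment status. The documents do not support that: 3.4 requires stable or responding disease, so as written treatment stops. The fault is that this conflicts with waiting for confirmation. A reader might also infer that the end of Cycle 2 always falls at least 60 - 42 = 18 days before PD may be called. That sets delayed cycles against an undelayed Day 60, which reads as the label of the end-of-Course-1 visit and would move with the delay.

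**Conclusion.** The point holds, at minor to moderate severity. The Cycle 2 timing does not fit the imaging schedule or the Day 60 bar. If the first restaging is meant, 6.3.1.3 and 6.3.3.1 give different progression references for growth of the target sum. In the illustration PD is called at 120 mm under one and at 150 mm under the other (138 mm on the later-low reading). These figures rest on assumed sums and on the assumed meaning of unconfirmed. The confirmatory scan also conflicts with removal and retreatment rules that stop treatment at first PD.

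The effect is on PD calls and treatment continuation. A reader might infer a biased response rate. The documents do not support that: PR keeps the original baseline, and best response is affected only by first-restaging PD followed by a confirmed response. That pattern should be uncommon. The documents give no rate for it, so no shift is claimed.

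**What to change.** 1. In 6.3.1.3 and 6.3.2.2, replace the Cycle 2 and Cycle 3 timing with: the first restaging (end of Course 1, the Day 60 evaluation).
2. Delete the re-baselining sentence in 6.3.1.3, so that the smallest sum on study is the only progression reference. If the sponsor prefers to keep it, state it as an exception in 6.3.3.1 and 6.3.4, and name the reference sum after the reset, including whether a later low replaces it.
3. In 6.3.2.2, name a scan that is on the calendar, for example PET/CT, and say whether confirmation is an exception to the new-lesion rule.
4. State whether removal for progression requires confirmed PD, and align the Précis, 3.1.2.1, 3.4, 3.5.4, 3.6 and Appendix 2 (footnote h). The best-response text should use the same definition.
5. Correct the pointer in 3.4 from 6.2 to 6.3.

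The cost is an amendment of wording. No scan is added beyond the confirmatory scan that 6.3.1.3 already requires, and sample size and decision rules are unchanged.
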